5.5. Lifestyle Considerations

The following guidelines are provided:

5.5.1. Meals and Dietary Restrictions

- Participants must abstain from all food and drink (except water) at least 4 hours prior to any safety laboratory evaluations (minimum of 12 hrs for lipid profile at screening). Participants will not be required to fast on Day 1 for post-dose laboratory safety tests. Water may be consumed without restriction throughout the study.
- On dosing days, a standard breakfast will be provided approximately 1 hour prior to the start of dosing and last approximately 20 minutes. Standard breakfast will be provided on other in-patient stay days.
- Lunch will be provided approximately 4 hours after the start of dosing.
- Dinner will be provided approximately 9 to 10 hours after the start of dosing.
- An evening snack may be permitted.
- While confined, the total daily nutritional composition should be approximately 55% carbohydrate, 30% fat and 15% protein. The daily caloric intake per participant should not exceed approximately 3200 kcal.

5.5.2. Caffeine, Alcohol and Tobacco

- Participants will abstain from alcohol for 24 hours prior to admission and continue abstaining from alcohol until discharge, as well as 24 hours prior to outpatient visits. Participants may undergo an alcohol breath, blood or urine test at the discretion of the investigator.
- Healthy participants will abstain from caffeine-containing products for 24 hours prior to the start of dosing or until collection of the final PK sample prior to discharge on Day 8. Caffeine is allowed for participants with ITP.
- Healthy participants will abstain from the use of tobacco- or nicotine-containing products for 24 hours prior to dosing and during confinement in the research unit. Nicotine-containing products are allowed for participants with ITP.

5.5.3. Activity

- Participants will be confined to the procedure room/participant room, as appropriate, for the first 8 hours after the start of dosing on Day 1 during continuous cardiac monitoring, except for lunch and to use the bathroom. After this, if the equipment setup allows, participants may be ambulatory during the continuous cardiac monitoring period, but should not engage in strenuous activities. If equipment does not allow ambulation, appropriate accommodations will be made by the investigator

site to facilitate continuous monitoring (eg, bedside urinals should be provided to accommodate participants' excretory needs).

- Participants will abstain from strenuous exercise (eg, heavy lifting, weight training, calisthenics, aerobics) for at least 48 hours prior to each blood collection for clinical laboratory tests. Walking at a normal pace will be permitted.

5.5.4. Contraception

The investigator or his or her designee, in consultation with the participant, will confirm that the participant has selected an appropriate method of contraception for the individual participant and his/her partner(s) from the permitted list of contraception methods (see [Appendix 4](#)) and will confirm that the participant has been instructed in its consistent and correct use. At time points indicated in the [SoA](#), the investigator or designee will inform the participant of the need to use highly effective contraception consistently and correctly and document the conversation and the participants affirmation in the participants chart (participants need to affirm their consistent and correct use of at least 1 of the selected methods of contraception). In addition, the investigator or designee will instruct the participant to call immediately if the selected contraception method is discontinued or if pregnancy is known or suspected in the participant or the participant's partner.

5.6. Screen Failures

Screen failures are defined as participants who consent to participate in the clinical study but are not subsequently randomly assigned to investigational product/entered in the study. Screen failure data are collected and remain as source and are not reported to the clinical database.

Individuals who do not meet the criteria for participation in this study (screen failure) may be rescreened once and must meet all inclusion/exclusion criteria. Rescreened participants will be re-consented. All screening assessments must be repeated during rescreening.

6. STUDY INTERVENTION

Study intervention is defined as any investigational intervention(s), marketed product(s), placebo, or medical device(s) intended to be administered to a study participant according to the study protocol.

For the purposes of this protocol, the term investigational product may be used synonymously with study intervention.

6.1. Study Intervention(s) Administered

For this study, the investigational product is PF-06755347 and its non-matching placebo.

PF-06755347 and non-matching placebo will be supplied by Pfizer as solution for injection in sterile vials for preparation of intravenous infusion and subcutaneous injections at the study site.

PF-06755347 1000 mg/vial Solution for Injection (50 mg/mL) is presented as a sterile solution for intravenous and subcutaneous administration. Each vial of PF-06755347 contains a sufficient amount of product to ensure an extractable volume of 20 mL of aqueous buffered solution, is sealed with a coated stopper and an overseal, and is labeled according to local regulatory requirements.

Placebo for PF-06755347 Solution for Injection is presented as a sterile solution for intravenous and subcutaneous administration. Each vial contains 20 mL of placebo as an aqueous buffered solution, is sealed with a coated stopper and an overseal, and is labeled according to local regulatory requirements.

Sterile vials will be supplied as individual vials packaged in an open-label fashion in units of multiple vials in a carton.

6.1.1. Administration

Healthy Participants

Participants will start receiving IP in a blinded fashion at approximately 08:00 hours (plus or minus 3 hours). Blinded investigator site personnel will administer IP for each participant according to the IP Manual. The IV infusion will be on the opposite arm from PK sampling and start and stop time of the infusion will be recorded. The preferred site for subcutaneous injection(s) will be on the abdomen.

Participants with ITP

Participants will receive open-label IP at approximately 08:00 hours (plus or minus 3 hours). Investigator site personnel will administer IP for each participant according to the IP Manual. The preferred site for subcutaneous injection(s) will be on the abdomen.

6.1.1.1. Guideline on Intravenous Infusion

PF-06755347 or placebo will be administered by continuous IV infusion. The infusion rate and duration depends on the dose and the volume to be infused. [Table 8](#) provides guidelines on infusion scheme for each proposed dose; however the actual infusion rate may be lowered and/or infusion duration may be increased to mitigate infusion-related symptoms at the discretion of the PI (see [Section 6.6](#) and [Section 6.7](#)). The overall infusion time will not exceed 4 hrs. The infusion scheme will also be adjusted appropriately if doses other than those proposed are used.

Table 8. Guideline on Intravenous Infusion Scheme

Target Dose (mg/kg)	Infusate Drug concentration (mg/mL)	Infusion Rate (mL/kg/min)	Dosing Rate (mg/kg/min)	Infusion Duration ^c (min)	Dose per Interval (mg/kg)
0.01	0.03	0.006	0.00018	60	0.01
0.03	0.03	0.017	0.00051	60	0.03
0.1	0.05	0.02	0.001	30	0.03
	0.05	0.04	0.002	35	0.07
0.3	0.15	0.02	0.003	30	0.09
	0.15	0.04	0.006	35	0.21
1 ^a	0.5	0.02	0.01	30	0.3
	0.5	0.04	0.02	35	0.7
1 ^b	0.5	0.011	0.0055	180	1
2	0.5	0.022	0.011	180	2
4	1.5	0.015	0.023	180	4
8	1.5	0.03	0.045	180	8
16	2.5	0.036	0.09	180	16

- Infusion rates for the first 3 participants in Cohort 5 (1 mg/kg IV).
- Infusion rates for the 4 participants in Cohort 5 (1 mg/kg IV) expansion.
- Infusion duration of 180 minutes (\pm 18 minutes).

6.1.1.2. Guideline on Subcutaneous Injection

For participants receiving a SC injection, the number of injections will be recorded. Time 0 for the SC injection will be the time of the first injection. The preferred body location for the SC injection is the abdomen but the 5 cm area around the navel should be avoided. If abdominal injections are not possible, arm or thigh locations may also be used. If an arm is used for the SC injection, the opposite arm should be used for the PK blood sample collections. For doses that require more than one injection, individual injections should be administered approximately 3 cm away from the site of the previous injection (ie, the abdomen, same arm or thigh). Avoid umbilicus area and skin with tattoos and scarring. The maximum volume for an individual injection is 1.5 ml. Since the drug product concentration is 50 mg/mL, the maximum number of injections will be approximately 4. At SC doses that require greater than the maximum number of injections, a SC infusion will be used.

If a participant experiences an infusion or injection site reaction during the administration period, then treatment administration should be paused for that participant and supportive care should be provided according to the Investigator's standard practice (eg, treatment with an antihistamine). Treatment administration may resume at the discretion of the Investigator if there are no systemic symptoms and if the reaction resolves.

Consult the IP Manual for detailed instructions regarding study drug preparation, stability and administration. Per the drug stopping rules ([Section 6.6](#) and [Section 6.7](#)), dosing will be paused for the entire cohort, for any serious adverse event (SAE) that occurs in a participant receiving active treatment until causality is fully assessed by the PI and Sponsor.

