6.6. Dose Progression

The participants within each cohort will be dosed using a sequential dosing scheme. For all cohorts, a single participant will be dosed at a given time, followed by a minimum of 72-hour (for IV) and 96-hours (for SC) safety monitoring period. In total there will be a minimum of 96 hours between each IV participant dosed and 120 hours for each SC participant dosed.

The following rules will be applied when considering dosing of the next participant in the cohort.

Sequential dosing may **proceed** only if no adverse events are reported OR all of the following criteria are met:

1. Any pro-inflammatory events are < Grade 2 Per CTCAE criteria in [Appendix 9](#).
2. All other adverse events are deemed mild or moderate in severity, regardless of relatedness.
3. Any laboratory, ECG or vital sign changes are considered not clinically significant.
4. No other pause or stop criteria are met.
5. For participants with ITP, in addition to the above criteria, no participant has greater than a 30% decrease in platelet count – defined from the immediate pre-dosing platelet count to the lowest postdosing platelet count. Dose progression will be independent of dose progression from HP cohorts at higher dose levels.

Sequential dosing should be **paused** if any criterion below is met in a participant receiving active drug:

1. Grade 2 (Objective) pro-inflammatory event (vomiting, diarrhea, hypotension or hypoxia) (see [Appendix 9](#)).
2. Adverse event which is considered to be severe (Grade 3 or higher) AND is deemed related to study intervention.
3. A moderate event (Grade 2) AND is deemed related to study intervention not otherwise identified as a proinflammatory event or AE of special interest, that in the opinion of the PI and Sponsor are of concern and warrant further investigation before additional dosing.
4. For participants with ITP, platelet count of <30 x 10⁹/L AND a decrease from baseline ≥30%, or a platelet count decrease from baseline of ≥50%, defined from the immediate pre-dosing platelet count to the lowest post-dosing platelet count, or a bleeding or bruising-related AE CTCAE 4.03 Grade 2 or higher (except metrorrhagia Grade 3 or higher).

Sequential dosing should be **stopped** at the current dose level if any criterion below is met in participant receiving active drug:

1. Grade 3 or greater pro-inflammatory event.
2. Serious adverse event that is deemed related to study intervention.

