
The investigator will make an assessment of intensity for each AE and SAE reported during the study and assign it to 1 of the following categories:
 
 • Mild: An event that is easily tolerated by the participant, causing minimal discomfort and not interfering with everyday activities. • Moderate: An event that causes sufficient discomfort and interferes with normal everyday activities. • Severe: An event that prevents normal everyday activities. An AE that is assessed as severe should not be confused with an SAE. Severe is a category utilized for rating the intensity of an event; and both AEs and SAEs can be assessed as severe. • An event is defined as “serious” when it meets at least 1 of the predefined outcomes as described in the definition of an SAE, NOT when it is rated as severe. 		

Assessment of Causality

- The investigator is obligated to assess the relationship between study intervention and each occurrence of each AE/SAE.
- A “reasonable possibility” of a relationship conveys that there are facts, evidence, and/or arguments to suggest a causal relationship, rather than a relationship cannot be ruled out.
- The investigator will use clinical judgment to determine the relationship.
- Alternative causes, such as underlying disease(s), concomitant therapy, and other risk factors, as well as the temporal relationship of the event to study intervention administration will be considered and investigated.
- The investigator will also consult the IB and/or product information, for marketed products, in his/her assessment.
- For each AE/SAE, the investigator **must** document in the medical notes that he/she has reviewed the AE/SAE and has provided an assessment of causality.
- There may be situations in which an SAE has occurred and the investigator has minimal information to include in the initial report to the Sponsor. However, **it is very important that the investigator always make an assessment of causality for every event before the initial transmission of the SAE data to the Sponsor.**
- The investigator may change his/her opinion of causality in light of follow-up information and send an SAE follow-up report with the updated causality assessment.
- The causality assessment is one of the criteria used when determining regulatory reporting requirements.

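### Section 6.1.1.2 credits Sections 6.6 and 6.7 with a cohort pause for any SAE until causality is assessed, but neither section lists that pause

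*Protocol*

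**What the plan says.** Protocol Section 6.1.1.2 (subcutaneous injection) opens its SAE sentence with "Per the drug stopping rules", citing Sections 6.6 and 6.7, and continues that "dosing will be paused for the entire cohort, for any serious adverse event (SAE) that occurs in a participant receiving active treatment". The hold runs "until causality is fully assessed by the PI and Sponsor". Severity and relatedness play no part in the trigger.

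Section 6.6 governs whether the next participant is dosed. Dosing may go ahead "only if no adverse events are reported OR all of the following criteria are met". Criterion 2 of that proceed list reads "All other adverse events are deemed mild or moderate in severity, regardless of relatedness" and makes no exception for serious events. Criterion 4 reads "No other pause or stop criteria are met". Among the stop criteria, number 2 is "Serious adverse event that is deemed related to study intervention", and number 3 makes confirmed drug-induced liver or kidney injury reportable as an SAE and dose limiting.

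Section 6.7 governs escalation. It points back to the 6.6 pause and stop criteria, and its own criterion that counts adverse events is limited to severe nonserious ones.

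Appendix 3 (Section 10.3.3) keeps seriousness and intensity apart: "An AE that is assessed as severe should not be confused with an SAE".

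**The concern.** A site reading Section 6.1.1.2 would expect to find, in 6.6 or 6.7, a pause triggered by seriousness and held open until causality is settled. If it is not there, two operative sections can give different instructions for the same event. Participants are dosed one at a time, and Section 2.1 says no further IV dosing will occur, so the subcutaneous section covers every remaining participant, including those with ITP. At stake is whether another person is dosed before the causality of an SAE on active drug is settled, and whether sites would act alike. Because Appendix 3 lets an SAE be mild or moderate, the case is not excluded by definition.

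**Working it through.** No sample size, error rate or estimate is involved, so the check compares the rules state by state.

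**Step 1: look for the cited pause.** Section 6.6 has four pause criteria, all for participants on active drug:

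1. a Grade 2 objective pro-inflammatory event;
2. a severe event that is deemed related;
3. a moderate event that is deemed related and that the PI and Sponsor consider of concern;
4. for ITP, defined platelet falls or bleeding and bruising events.

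None is triggered by seriousness, and none is a hold pending causality. The SAE entries in 6.6 are stop criteria 2 and 3. Section 6.7 adds no SAE pause. Its remaining entries concern ending escalation, some of them at the team's discretion. The rule is therefore absent from both sections cited for it.

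**Step 2: run an SAE through both sections.** Take an SAE on active drug that meets no other 6.6 criterion: not a pro-inflammatory event of Grade 2 or above, not confirmed liver or kidney injury, not an ITP platelet or bleeding event, and without clinically significant laboratory, ECG or vital sign change.

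| State of the SAE | Section 6.1.1.2 | Section 6.6 | Result |
|---|---|---|---|
| Mild or moderate, joint causality assessment incomplete and not deemed related | Pause the cohort | Proceed criteria met; no pause or stop criterion met | Contradiction |
| Mild or moderate, assessed as unrelated by PI and Sponsor | Pause has ended | Proceed criteria met | Agree |
| Severe, joint causality assessment incomplete and not deemed related | Pause the cohort | Proceed criterion 2 fails; no pause or stop criterion met | 6.6 names no action |
| Severe, assessed as unrelated by PI and Sponsor | Pause has ended | Proceed criterion 2 fails; no pause or stop criterion met | No named action and no stated route to resume |
| Any severity, deemed related | Pause until causality is assessed | Stop; 6.7 then ends escalation | Dosing is held under both; 6.6 supplies the stop |

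**Step 3: compare the conditions for resuming.** Under 6.1.1.2 the hold ends when the PI and Sponsor have completed the causality assessment. Under 6.6, any dose pause goes to the dose escalation subteam, which looks at whether symptoms have resolved and IL-6 is back near baseline; the PI has the final decision on dosing. A cohort paused for an SAE under 6.1.1.2 could meet one condition and not the other, and the protocol does not say which applies.

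**The case against.** The best defence reads the sections in sequence. Stopping for an SAE deemed related presupposes a causality assessment, 6.1.1.2 holds dosing while it is made, and proceed criterion 4 is broad enough to take in a pause stated elsewhere. The 6.6 wording is permissive and the 6.1.1.2 wording mandatory, so a site can satisfy both by pausing. That is a sensible way to act, but it does not repair the text. Section 6.1.1.2 presents its pause as derived from 6.6 and 6.7, so using criterion 4 to bring 6.1.1.2 into 6.6 is circular.

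A second defence is that pending causality is short-lived. Section 8.3.1.1 requires SAEs to be reported within 24 hours, and Section 10.3.3 requires the investigator's causality call before first transmission. This narrows the gap. It does not close it, because 6.1.1.2 also needs the Sponsor's assessment, for which no time is given. Section 10.3.3 does treat unknown causality as related, but only for reporting. If that were carried into 6.6, the result would be a stop, which is still not the pause described in 6.1.1.2.

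Other controls also stand: each participant's 96-hour data are reviewed before the next subcutaneous dose, Section 4.1 lets any PI extend that review, and the subteam cannot overrule the PI. So 6.6 allows the next dose and does not compel it.

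A reader might also infer that 6.1.1.2 imposes an unconditional pause and so conflicts with 6.6 even for an SAE already found unrelated. The documents do not support that: the hold ends with the causality assessment, and for a mild or moderate event the two sections then agree.

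**Conclusion.** The point holds in a bounded form. The pause that 6.1.1.2 attributes to 6.6 and 6.7 is not in either section. Three consequences follow:

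- one direct contradiction, for a mild or moderate SAE that meets no other 6.6 criterion while the joint causality assessment is incomplete;
- one gap, for a severe SAE not deemed related, where 6.6 blocks the proceed rule but names no action;
- two different release conditions for a pause.

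This rests on reading an SAE whose causality is open as not yet deemed related, and on the event falling outside the other 6.6 criteria. Those criteria are wider than severity and relatedness: they also cover laboratory, ECG, vital sign, platelet and bleeding findings, and seriousness enters through two stop criteria. Many real SAEs would be caught by one of them.

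The documents give no basis for a duration. A reader might subtract the 96-hour review from the 120-hour minimum interval and call the 24-hour difference the period of conflict. That is not what it measures: an SAE can arise before or after the review, the interval is only a minimum, and the conflict lasts as long as causality is open.

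This should be corrected because it concerns dosing in a first-in-human study and is cheap to settle. It does not show that participants would in practice be dosed through an unresolved SAE.

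**What to change.** Reconcile Sections 6.1.1.2, 6.6 and 6.7. State one SAE rule in the Section 6.6 pause and stop lists that says what happens when an SAE on active drug is related, unrelated or awaiting causality, at each level of severity, so that the severe, unrelated case has a named action. Say in the same place which release condition applies: the completed causality assessment, the subteam's review of symptoms and IL-6, or both. Reduce the sentence in 6.1.1.2 to a reference to that rule, and check that the 6.7 references back to 6.6 still work.

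Which rule stands is a clinical decision for the sponsor and investigators; this review takes no position on it. The cost is a criterion in 6.6 and a sentence in 6.1.1.2, carried in a protocol amendment. If a hold pending causality is retained, the operational downside is at most an occasional short delay.

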6.2. Preparation/Handling/Storage/Accountability

1. The investigator or designee must confirm appropriate temperature conditions have been maintained during transit for all study interventions received and any discrepancies are reported and resolved before use of the study intervention, as applicable for temperature-monitored shipments.
2. Only participants enrolled in the study may receive study intervention and only authorized site staff may supply or administer study intervention. All study interventions must be stored in a secure, environmentally controlled, and monitored (manual or automated recording) area in accordance with the labeled storage conditions with access limited to the investigator and authorized site staff. At a minimum, daily minimum and maximum temperatures for all site storage locations must be documented and available upon request. Data for nonworking days must indicate the minimum and maximum temperature since previously documented for all site storage locations upon return to business.
3. The investigator, institution, or the head of the medical institution (where applicable) is responsible for study intervention accountability, reconciliation, and record maintenance (ie, receipt, reconciliation, and final disposition records). All study interventions will be accounted for using an investigational product accountability form/record.
4. Further guidance and information for the final disposition of unused study interventions are provided in the IP manual.
5. Any storage conditions stated in the SRSD will be superseded by the storage conditions stated on the product label.
6. Study interventions should be stored in their original containers and in accordance with the labels.
7. See the IP Manual for storage conditions of the study intervention once prepared.
8. Deviations from the storage requirements, including any actions taken, must be documented and reported to Pfizer upon discovery. The site should actively pursue options for returning the study intervention to the storage conditions described in the labeling, as soon as possible. Once an excursion is identified, the study intervention must be quarantined and not used until Pfizer provides permission to use the study intervention. It will not be considered a protocol deviation if Pfizer approves the use of the study intervention after the temperature excursion. Use of the study intervention prior to Pfizer approval will be considered a protocol deviation. Specific details regarding the definition of an excursion and information the site should report for each excursion will be provided to the site in the IP manual.

9. The Sponsor or designee will provide guidance on the destruction of unused study intervention (eg, at the site). If destruction is authorized to take place at the investigator site, the investigator must ensure that the materials are destroyed in compliance with applicable environmental regulations, institutional policy, and any special instructions provided by Pfizer, and all destruction must be adequately documented.

